9.2 Clinical Procedures and Assessments

9.2.1 Full Physical Exam

Physical examination will consist of the following body systems: (1) eyes; (2) ears, nose, throat; (3) cardiovascular system; (4) respiratory system; (5) gastrointestinal system; (6) dermatologic system; (7) extremities; (8) musculoskeletal system; (9) nervous system; (10) lymph nodes; (11) other.

9.2.2 Height and Weight

A subject should have weight and height measured with shoes off. Height is recorded in centimeters (cm) without decimal places by rounding. Weight is collected in kilograms (kg) with 1 decimal place.

9.2.3 BMI

BMI is calculated using the formula provided below.

$$\text{BMI} = \text{weight (kg)} / \text{height (m)}^2$$

BMI should be reported to 1 decimal place by rounding. The inclusion criterion for BMI will be assessed based on a rounded value.

9.2.4 Vital Signs

Vital signs will include sitting systolic blood pressure and diastolic blood pressure (resting more than 5 minutes) (mmHg), sitting pulse rate (beats per minute), and body temperature (axillary) (°C).

When vital signs are scheduled at the same time as blood draws, the blood draw will take priority and vital signs will be obtained within an acceptable time window (see [Appendix B](#)).

9.2.5 12-Lead ECG

A resting 12-lead ECG will be recorded. The investigator or sub-investigator (or a qualified physician at the study site) will interpret the ECG findings using one of the following categories: within normal or abnormal. In the case that the ECG findings are abnormal, the investigator or sub-investigator (or a qualified physician at the study site) will judge if it is clinically significant. The following parameters will be recorded on the eCRF from the subject's ECG trace: heart rate, RR interval, PR interval, QT interval, QRS interval, and QTc interval (corrected by the Fridericia's formula).

When 12-lead ECG measurements are scheduled at the same time as blood draws, the blood draw will take priority and 12-lead ECGs will be obtained within an acceptable time window (see [Appendix B](#)).

9.2.6 Study Drug Administration

Each subject will receive TAK-536 pediatric formulation under one of the following treatment conditions in each period.

1. One sachet of TAK-536 10 mg granules (TAK-536 10 mg) will be administered orally with 200 mL of water in the morning under fasted condition (fasted overnight for at least 10 hours prior to study drug administration).
2. One sachet of TAK-536 10 mg granules (TAK-536 10 mg) will be administered orally with 200 mL of water in the morning under fed condition (at 30 minutes after starting breakfast).

9.2.7 AE Monitoring

AE monitoring begins after the signing of informed consent. A complete description of AE collections and procedures is provided in Section [10.2](#).

9.2.8 Laboratory Procedures and Assessments

All samples will be collected in accordance with the separately defined laboratory procedures. Laboratory samples will be taken following a minimum 8 hour overnight fast on the days stipulated in the study schedule (see Section [3.0](#)).

9.2.8.1 Clinical Laboratory Tests

Hematology

Hematology will consist of the following tests:

Red blood cells (RBC)	Hemoglobin
White blood cells (WBC) with differential (neutrophils, basophils, eosinophils, lymphocytes, monocytes)	Hematocrit
	Platelets

Serum Chemistry

Serum Chemistry evaluations will consist of the following standard chemistry panel:

ALT	Sodium
AST	Chloride
ALP	Calcium
GGT	Inorganic phosphorus
Total bilirubin	Total cholesterol
Total protein	Fasting triglyceride
Albumin	Uric acid
Creatinine	LDH
BUN	Creatine kinase
Potassium	Fasting glucose

Urinalysis

Urinalysis will consist of the following tests:

pH	Qualitative tests for glucose, protein, occult blood, ketone body, bilirubin, and urobilinogen
Specific gravity	

Other

Only for eligibility assessment:

Serum (immunology tests)	Urine (urine drug tests)
HBsAg, HCV antibody, HIV antibody/antigen, serum test for syphilis	phencyclidine, benzodiazepines, cocaine, antihypnotic agents, cannabinoids, opioids, barbiturates, and tricyclic antidepressants

HBsAg=hepatitis B surface antigen, HCV=hepatitis C virus, HIV=human immunodeficiency virus.

Note: The investigator or sub-investigator will inform the results of immunology and urine drug tests directly to subjects. The Sponsor will confirm the overall test results ("Positive" or "All negative"), rather than detailed results, for subjects (including reserve subjects) to be administered the study drug.

The local laboratory will perform laboratory tests for hematology, serum chemistry, and urinalysis. The results of laboratory tests will be returned to the investigator or sub-investigator, who is responsible for reviewing and filing these results.

If subjects experience ALT or AST $>3\times$ ULN, follow-up laboratory tests (at a minimum, ALP, ALT, AST, total bilirubin, GGT, and INR) should be performed within a maximum of 7 days and preferably within 48 to 72 hours after the abnormality was noted (Refer to Section 7.6 and Section 10.2.9.4 for the appropriate guidance on reporting abnormal liver function tests).

The investigator will maintain a copy of the reference ranges for the laboratory used.

All clinically significant laboratory abnormalities must be recorded as an AE in the subject's source documents and on the appropriate eCRF. A clinically significant laboratory abnormality that has been verified by retesting will be followed until the abnormality returns to an acceptable level or a satisfactory explanation has been obtained.

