11.1.4.2 Clinical Laboratory Evaluation

For continuous variables, the observed values and the changes from baseline will be summarized by treatment condition for each time point using descriptive statistics. Case plots for the observed values will also be provided for each treatment condition.

For categorical variables, shift tables showing the number of subjects in each category at baseline and each post-baseline time point will be provided for each treatment condition.

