#### **7.11.2.2 Urinalysis**

Analysis Set: Safety Analysis Set  
Analysis Variable(s): Specific Gravity  
pH  
Glucose  
Protein  
Blood  
Ketone Body  
Bilirubin  
Urobilinogen  
Categories: Results of determination based on reference values  
[Below lower limit of reference value,  
Within the range of reference value,  
Over upper limit of reference value]  
Visit: Predose, 24 and 48 Hours Postdose, Follow-up Examination (Day 6)  
Analysis Method(s): For specific gravity, summaries (1) to (3) will be provided by treatment condition.  
For each variable other than specific gravity, summary (3) will be provided by treatment condition.  
(1) Descriptive statistics for observed values for each visit and changes (each visit after administration-predose) will be provided.  
(2) Case Plots  
(3) A shift table for each visit before and after administration will be provided for the results of determination based on the reference values.

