### **7.13 Changes in the Statistical Analysis Plan**

The analysis plan described in this Statistical Analysis Plan is the same as the analysis plan described in the protocol.

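### Urine pH does not get the numeric summaries that the protocol gives continuous laboratory variables, and the only table for the six qualitative urine tests merges all abnormal grades

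*Protocol*

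**What the plan says.** Protocol 9.2.8.1 lists eight urinalysis variables: pH, specific gravity, and six grouped as "Qualitative tests for glucose, protein, occult blood, ketone body, bilirubin, and urobilinogen".

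Protocol 11.1.4.2 sets two rules for laboratory data and exempts no urine variable:

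- Continuous: "For continuous variables, the observed values and the changes from baseline will be summarized by treatment condition for each time point using descriptive statistics". It adds: "Case plots for the observed values will also be provided for each treatment condition".
- Categorical: "For categorical variables, shift tables showing the number of subjects in each category at baseline and each post-baseline time point will be provided". It does not say what the categories are.

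SAP 7.11.2.2 lists all eight variables under one three-level classification: below, within or over the reference limits. It defines three displays: (1) descriptive statistics of observed values and changes from predose, (2) case plots, and (3) a shift table on the three-level classification. Specific gravity gets all three. For the rest: "For each variable other than specific gravity, summary (3) will be provided by treatment condition".

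SAP 7.13 states: "The analysis plan described in this Statistical Analysis Plan is the same as the analysis plan described in the protocol".

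**The concern.** There are two separate points, of different strength.

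The first concerns pH. It is a number, and the protocol lists it beside specific gravity and outside the qualitative group. The SAP treats specific gravity as continuous but not pH. Under the protocol's rule pH should have descriptive statistics, changes and case plots. Under the SAP it has none of these, and the section meant to record departures says there are none.

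The second concerns the six qualitative tests. A shift table on reference status puts every abnormal grade in one cell. A subject who goes from a low to a high grade of, say, protein or occult blood after dosing is counted as over reference at both visits, that is, as unchanged. A subject who starts normal is shown as shifting, but the table does not say how far.

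Urinalysis belongs to the secondary safety endpoint, and the secondary objective is the food effect on safety. For seven of the eight urine variables this shift table is the only display the SAP plans. It specifies subject listings for PK parameters but none for laboratory results.

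**Working it through.** **Part 1: pH.** The plan states no figure here, so the check sets the texts side by side.

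| Variable | Listed as qualitative in Protocol 9.2.8.1 | Displays in SAP 7.11.2.2 |
|---|---|---|
| Specific gravity | No | (1), (2), (3) |
| pH | No | (3) only |
| Glucose, protein, occult blood, ketone body, bilirubin, urobilinogen | Yes | (3) only |

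Variables with display (3) only: 1 + 6 = 7 of 8. The protocol never labels pH continuous. That is an inference from three facts: pH is numeric, it stands outside the qualitative group, and the SAP handles its neighbour in the list as continuous. If the inference is accepted, displays (1) and (2) are missing for one variable and SAP 7.13 is inaccurate on that variable.

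**Part 2: what the three-level table hides.** The documents give neither the laboratory's reporting grades nor the cut-off for normal, so both are assumed and varied. Let m be the number of grades within reference and k the number above it.

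- Possible worsening transitions: (m + k)(m + k − 1)/2
- Visible (normal to abnormal): m × k
- Hidden among abnormal grades: k(k − 1)/2
- Hidden inside the reference range: m(m − 1)/2

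| Assumed scale (within \| over reference) | m | k | Possible | Visible | Hidden among abnormal | Hidden within normal |
|---|---|---|---|---|---|---|
| − \| + | 1 | 1 | 1 | 1 | 0 | 0 |
| − \| 1+, 2+ | 1 | 2 | 3 | 2 | 1 | 0 |
| − \| 1+ to 3+ | 1 | 3 | 6 | 3 | 3 | 0 |
| −, ± \| 1+ to 3+ | 2 | 3 | 10 | 6 | 3 | 1 |
| − \| ±, 1+ to 3+ | 1 | 4 | 10 | 4 | 6 | 0 |
| −, ± \| 1+ to 4+ | 2 | 4 | 15 | 8 | 6 | 1 |
| − \| ±, 1+ to 4+ | 1 | 5 | 15 | 5 | 10 | 0 |

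Worked example for − | ±, 1+ to 3+: possible 5 × 4/2 = 10; visible 1 × 4 = 4; hidden 4 × 3/2 = 6.

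So nothing is lost under plain negative/positive reporting, and something is always lost once there are two abnormal grades. The visible transitions are also blurred: with k of 2 or more, a move from normal to the lowest abnormal grade and one to the highest fall in the same cell. A table by reported grade would hide none of these transitions.

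These are counts of possible transitions, not expected frequencies.

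**The case against.** The strongest reply is that the SAP does what the protocol asks for the six qualitative tests. A reader might infer that Protocol 11.1.4.2 requires shift tables by reported grade and that the SAP contradicts it. The text does not support that. The promise is "For categorical variables, shift tables showing the number of subjects in each category at baseline and each post-baseline time point", with the categories left open, and Protocol 11.1 assigns the definition of analysis variables to the SAP. The SAP defines three categories and supplies the table. This objection stands in full: for these six tests the point is lost information, and SAP 7.13 is not wrong about them.

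On pH, it can be said that the protocol does not call it continuous, that it still gets a shift table in which both limits mean something, and that no safety question is named which mean urine pH would answer. That limits the importance. It does not explain why pH and specific gravity are handled differently, or why the difference is undeclared.

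On impact, the objection largely stands. A shift among abnormal grades needs an abnormal predose result. Subjects are healthy men aged 20 to 35, and exclusion criteria 4 and 17 remove clinically significant renal or metabolic disease and laboratory values suggesting underlying disease at Screening or before Period 1 dosing. Normal to abnormal, the likelier change, is visible. Protocol 9.2.8.1 also requires clinically significant laboratory abnormalities to be recorded as adverse events, and the SAP tabulates those by treatment condition. What remains is that this route depends on the investigator's judgement of significance, and that the size of a shift from normal is still not shown.

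The low-side category has no clear meaning for most of the qualitative tests, but an unused cell does no harm.

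**Conclusion.** Both parts hold, as minor points.

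For pH there is a mismatch between SAP and protocol that SAP 7.13 does not declare: one variable lacks descriptive statistics, change from predose and case plots. It rests on reading pH as continuous, which is a reasonable inference but not stated.

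For the six qualitative tests there is an avoidable loss of detail in the only planned display. Its size depends on the unstated grading scale: from 0 of 1 worsening transitions hidden (negative/positive), through 3 of 6 (− | 1+ to 3+) and 6 of 10 (− | ±, 1+ to 3+), to 10 of 15 (− | ±, 1+ to 4+).

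A reader might take the upper end of that range to mean that most real worsening would be missed. The documents do not support this. The scale is assumed, possible transitions are not equally likely, and most subjects should start normal. Nor would a clinically significant change disappear from the report, since it would appear as an adverse event. The primary PK analysis is not affected.

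**What to change.** In SAP 7.11.2.2:

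- Add pH to summaries (1) and (2) alongside specific gravity. If the sponsor prefers not to, record the departure and its reason in SAP 7.13.
- Produce the shift tables for the six qualitative tests by the grade the laboratory reports, and state that scale in the SAP. The reference-based table can be kept as well.

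SAP 7.11.4 offers a precedent: ECG interpretation is tabulated in its own categories, with two kinds of abnormal kept apart.

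The cost is SAP wording and a few more table rows. The urine tests are already collected, and no procedure or visit changes.

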9.3 PK Samples

Blood samples for PK analysis of TAK-536 will be collected according to the study schedule specified in Section 3.0. Instructions for sample processing and shipment are provided in a separately defined procedure.

9.3.1 PK Measurements

The following PK parameters of unchanged TAK-536 will be determined from the plasma concentration-time profile up to 48 hours after the study drug administration based on non-compartmental analysis. Actual sampling times, instead of scheduled sampling times, will be used in all PK computations.

The following PK parameters will be calculated from plasma concentrations of TAK-536, unless otherwise specified:

Symbol/Term	Definition
Plasma	
AUC _{last}	Area under the plasma concentration-time curve from time 0 to time of the last quantifiable concentration.
AUC _∞	Area under the plasma concentration-time curve from time 0 to infinity.
C _{max}	Maximum observed plasma concentration (observed value).
t _{max}	Time of first occurrence of C _{max} (observed value).
MRT	Mean residence time.
λ _z	Terminal disposition phase rate constant.
t _{1/2z}	Terminal disposition phase half-life.
CL/F	Apparent clearance after extravascular administration.
V _{z/F}	Apparent volume of distribution during the terminal disposition phase after extravascular administration.

9.3.1.1 Plasma for PK Measurements

Blood samples (one 3-mL sample per scheduled time) for PK analysis of unchanged TAK-536 will be collected into Vacutainers containing ethylenediaminetetraacetic acid dipotassium salt dihydrate (EDTA-2K) according to the schedule specified in [Table 9.a](#).

Table 9.a Collection of Plasma Samples for PK Analysis

Analyte	Sample Type	Dosing Day (Periods 1 and 2)	Scheduled Time
Unchanged TAK-536	Plasma	Day 1 of each period	Predose, 0.5, 1, 1.5, 2, 2.5, 3, 3.5, 4, 5, 6, 8, 12, 16, 24, and 48 hours postdose

The actual time of sample collection will be recorded on the source document and eCRF.

If the subject is prematurely terminating from the study within 48 hours after the study drug administration, the blood sample for unchanged TAK-536 measurement will be collected at early termination.

9.3.2 Confinement

Subjects will be admitted to the study site on the day before the study drug administration (Day -1) in both Periods 1 and 2, and will be hospitalized under medical supervision for 4 days (until 48 hours after the study drug administration). They will undergo daily examinations from the day before the study drug administration (Day -1) and observations during their hospitalization according to the study schedule specified in Section 3.0, and will be discharged from the study site on Day 3 after confirmation of safety by the investigator or sub-investigator.

10.0 ADVERSE EVENTS

10.1 Definitions and Elements of AEs

An AE is defined as any untoward medical occurrence in a clinical investigation subject who has signed informed consent to participate in a study; it does not necessarily have to have a causal relationship with the treatment or study participation.

An AE can therefore be any unfavorable and unintended sign (eg, a clinically significant abnormal laboratory finding), symptom, or disease temporally associated with the study participation, whether or not it is considered related to the drug or study procedures.

An untoward finding generally may:

- Indicate a new diagnosis or unexpected worsening of a pre-existing condition. (Intermittent events for pre-existing conditions or underlying disease should not be considered AEs.)
- Necessitate therapeutic intervention.
- Require an invasive diagnostic procedure.
- Require discontinuation or a change in dose of study drug or a concomitant medication.
- Be considered unfavorable by the investigator or sub-investigator for any reason.

Diagnoses versus signs and symptoms:

- Each event should be recorded to represent a single diagnosis. Accompanying signs (including abnormal laboratory values or ECG findings) or symptoms should NOT be recorded as additional AEs. If a diagnosis is unknown, sign(s) or symptom(s) should be recorded appropriately as an AE(s).

Laboratory values and ECG findings:

- Changes in laboratory values or ECG parameters may be considered AEs if they are judged to be clinically significant (ie, if some action or intervention is required or if the investigator or sub-investigator judges the change to be beyond the range of normal physiologic fluctuation). A laboratory re-test and/or continued monitoring of an abnormal value are not considered an intervention. In addition, repeated or additional noninvasive testing for verification, evaluation or monitoring of an abnormality is not considered an intervention.
- If abnormal laboratory values or ECG findings are the result of pathology for which there is an overall diagnosis (eg, increased creatinine in renal failure), the diagnosis only should be reported appropriately as an AE.

Pre-existing conditions:

- A pre-existing condition (present at the time of signing of informed consent) is considered a concurrent medical history condition and should NOT be recorded as an AE. The first examination after the informed consent (eg, laboratory test, ECG, X-ray, etc) should NOT be recorded as an AE unless related to a study procedure. However, if the subject experiences a

worsening or complication of such a concurrent medical history condition, the worsening or complication should be recorded appropriately as an AE (worsening or complication occurs after informed consent is signed). The investigator or sub-investigator should ensure that the event term recorded captures the change in the condition (eg, “worsening of...”).

- If a subject has a pre-existing episodic condition (eg, asthma, epilepsy), any occurrence of an episode should only be captured as an AE if the episodes become more frequent, serious, or severe in nature. The investigator or sub-investigator should ensure that the AE term recorded captures the change from baseline in the condition (eg, “worsening of...”).
- If a subject has a degenerative concurrent condition (eg, cataracts, rheumatoid arthritis), worsening of the condition should only be captured as an AE if occurring to a greater extent to that which would be expected. The investigator or sub-investigator should ensure that the AE term recorded captures the change in the condition (eg, “worsening of...”).

Worsening of AEs:

- If the subject experiences a worsening or complication of an AE after the first administration of study drug or after any change in study drug, the worsening or complication should be recorded as a new AE. Investigators or sub-investigators should ensure that the AE term recorded captures the change in the condition (eg, “worsening of...”).

Changes in severity of AEs:

- If the subject experiences a change in the severity of an AE that is not associated with a change in study drug, the event should be captured once with the maximum severity recorded.

Pre-planned surgeries or procedures:

- Pre-planned procedures (surgeries or therapies) that were scheduled prior to the signing of informed consent are not considered AEs. However, if a pre-planned procedure is performed early (eg, as an emergency) due to a worsening of the pre-existing condition, the worsening of the condition should be captured appropriately as an AE. Complications resulting from any planned surgery should be reported as AEs.

Elective surgeries or procedures:

- Elective procedures (surgeries or therapies) performed where there is no change in the subject’s medical condition should not be recorded as AEs but should be documented in the subject’s source documents. Complications resulting from an elective surgery should be reported as AEs.

Overdose:

- An overdose is defined as a known deliberate or accidental administration of study drug, to or by a study subject, at a dose above that which is assigned to that individual subject according to the study protocol. It is up to the investigator or sub-investigator to decide whether a dose is to be considered an overdose, in consultation with the Sponsor.

- All cases of overdose (with or without associated AEs) will be documented on an Overdose page of the eCRF, in order to capture this important safety information consistently in the database. AEs associated with an overdose will be documented on an AE page of the eCRF according to Section [10.0](#).
- Serious adverse events (SAEs) of overdose should be reported according to the procedure outlined in Section [10.2.9](#).
- In the event of drug overdose, the subject should be treated symptomatically.

